### **DATA ANALYSIS**

General principles for data analysis are provided below.

Safety analyses will be conducted in all patients overall and in subgroups defined by age and status of inhibitor as well as by severity for patients without inhibitors, using all authorized emicizumab dosing regimens. Proportions of patients developing each type of AE (e.g., TE, TMA, and anaphylaxis) are calculated along with the corresponding 95% CIs, and are reported for all patients as well as in age-defined subgroups including newborns with or without inhibitors.

Bleed outcomes analyses will be conducted in all patients overall and in subgroups defined by age and status of inhibitor as well as by severity for patients without inhibitors. Mean ABR with standard deviation and percentage of patients with zero bleeds are reported overall and in subgroups defined by age and status of inhibitor as well as by severity for patients without inhibitors. Summary statistics are provided overall and for the relevant subgroups.

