## **8.5 STUDY SIZE**

The sample size depends on the approval and uptake of emicizumab in the countries with centers participating in the PedNet Registry. As of January 2019, PedNet enrolled 1795 patients with hemophilia A, of which 1173 patients had severe disease, 225 patients had moderate disease and 397 had mild disease. Of the patients with severe disease, 351 patients had inhibitor diagnosed between 2000 and 2019.

Assuming a constant sample size of patients with severe disease in the registry (N=1173 with severe disease regardless of FVIII inhibitor and N=351 with inhibitor), and assuming that at least 50% of these patients receive emicizumab during the 6 years of the study, the anticipated sample size is expected to be n=587 for patients with severe disease and n=176 for patients with inhibitor at the end of this 6-year study.

No data about inhibitor status is available at this stage for patients with moderate disease. Assuming a constant sample size of patients with moderate disease in the registry (N=225 with moderate disease regardless of FVIII inhibitor), and assuming that at least 15% of these patients receive emicizumab during the 6 years of the study, the anticipated sample size is expected to be n=34 for patients with moderate disease.

The table below presents possible sample sizes with the average adoption of the drug varies between 15%–75% for severe patients and 5-25% for moderate patients during the study.

The MAH acknowledges that these estimates may change if the total number of patients enrolled in the registry changes significantly during the study time. As per last interim CSR (28-Sep-2022), a total of 266 patients enrolled since the beginning of the PedNet Registry up until the clinical cutoff date of 31 December 2021 were reported to have started treatment with emicizumab (regardless of the severity). Of these, 216 patients had updated follow-up data until 31 December 2021 and were included in the CSR (80 patients with inhibitors, 132 patients without inhibitors, and 4 patients with unknown inhibitor status).

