## 8.7 DATA ANALYSIS

### Data transformation

The MAH will receive aggregate level data of patients treated with emicizumab from the PedNet Registry on an annual basis.

Based on the number of patients, number of AEs, and exposure to emicizumab provided by the Registry, the MAH will perform analyses of frequencies/incidence of AEs overall and grouped by age and status of inhibitor as well as by severity for patients without inhibitors. The youngest age group will be newborn (birth to 28days). Other age groups include: 29 days-<6 months, 6 months-<2 years, 2 years-<6 years, 6 years-<12 years, 12 years-18 years. The MAH will report ABR for treated bleeds, percentages of zero bleeds, ABR for joint bleeds and major bleeds overall and grouped by age and status of inhibitor as well as by severity for patients without inhibitors as sent by PedNet registry. ABRs for soft tissue bleeds and minor bleeds is not calculated by PedNet and therefore only the number of bleeds will be presented.

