### 8.7.1 Primary Analyses

The primary AEs are TE, TMA, and anaphylaxis. Additional AEs including inhibitor development and unexpected poor efficacy will be included as they are collected by PedNet Registry.

Adverse events collected in PedNet are not collected according to MedDRA classification. Most events are collected according to pre-specified lists; however, free-text fields are also available for each event. Whenever possible, AEs will be reclassified by Roche according to MedDRA PT level using the most current MedDRA version.

Primary analyses: For each AE of interest (TMA, TE, and anaphylaxis), the following analysis will be performed overall and grouped by age and status of inhibitor as well as by severity for patients without inhibitors:

- Annual incidence rate of the AE among patients exposed to emicizumab will be estimated as the number of patients who were treated with emicizumab and developed the AE, divided by the person years of emicizumab exposure. The numerator will be calculated using report from PedNet.
- PedNet will provide number of patients treated with emicizumab and emicizumab mean exposure days, which will be used to calculate the person years of emicizumab exposure using the following formula:

Person years of emicizumab exposure=[number of patients exposed to emicizumab×mean emicizumab exposure time in days–number of patient exposed to emicizumab and had event×(mean emicizumab exposure time in days/2\*)]/365.25

\*Note that this calculation accounts for patients who are censored in the study once they have experienced an adverse event (event is imputed to happen after half the exposure time).

Exact binomial 95% confidence intervals will be calculated for each incidence rate.

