### **8.7.2            Secondary analyses:**

- Annual incidence proportion of AE of interest (TMA, TE, and anaphylaxis) among patients exposed to emicizumab will be estimated as the number of patients who were treated with emicizumab and developed the AE, divided by the number of patients who are exposed to emicizumab. The incidence proportion will be calculated overall and by age and status of inhibitor as well as by severity for patients without inhibitors.
- For each AE of interest (TMA, TE, and anaphylaxis), the following proportions will be calculated, together with the corresponding 95% confidence intervals:
  - Annual incidence proportions of the AE among patients treated with emicizumab and concurrently with each of the following drugs: aPCC, rFVIIa, and FVIII product.
- Annual number and percentage of each of the other adverse events reported to PedNet will be presented. Currently, in addition to TE, TMA, and anaphylaxis, these events may include: new inhibitors, allergic reactions, local subcutaneous reaction, other AEs including unexpected poor efficacy.
- ABRs: Estimates for the ABR are based on a negative-binomial model adjusted for age group and inhibitor status. The negative-binomial models each use the “total number of bleeds” (for each specified type of bleed) as the outcome and the model is offset by the “total duration of follow-up” since first exposure to emicizumab.

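### Section 8.7.1 prescribes exact binomial intervals for a person-year rate and does not say what the binomial n is; an exact Poisson interval is needed

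*Protocol*

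**What the plan says.** Protocol section 8.7.1 sets the primary analysis for thromboembolic events (TE), thrombotic microangiopathy (TMA) and anaphylaxis. The annual incidence rate is "estimated as the number of patients who were treated with emicizumab and developed the AE, divided by the person years of emicizumab exposure". Person-years come from the number of patients and their mean exposure days, less half the mean exposure for each patient with the event, because the "event is imputed to happen after half the exposure time". The section closes with "Exact binomial 95% confidence intervals will be calculated for each incidence rate". It does not say whether patients or person-years serve as the binomial n, and it gives no rescaling.

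Section 8.7.2 defines a separate, secondary incidence proportion: patients who "developed the AE, divided by the number of patients who are exposed to emicizumab". The Data Analysis part of the synopsis ties its intervals to proportions: "Proportions of patients developing each type of AE (e.g., TE, TMA, and anaphylaxis) are calculated along with the corresponding 95% CIs". No section names an interval for events over person-time.

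The primary analysis is to be run overall and by age, inhibitor status and, for patients without inhibitors, severity. On age, section 8.7 says "The youngest age group will be newborn (birth to 28days".

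**The concern.** An exact binomial interval describes x successes in a whole number of trials, with a parameter between 0 and 1. The primary denominator is person-years, which are continuous, and a rate per person-year may exceed 1. The term rate cannot be read loosely as a proportion, because 8.7.2 defines the proportion separately. Nor is this a detail left to an analysis plan: the protocol names a method, and the method does not match the measure.

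The main aim is safety and no hypothesis test is specified, so the interval is the main statement of uncertainty. If few or no TE, TMA or anaphylaxis events occur, the upper limit carries most of the message. An analyst following 8.7.1 must guess what n is, and the guesses give different limits.

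**Working it through.** The protocol states no rate, interval or precision target for this endpoint, so there is no figure to reproduce.

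**Inputs from the protocol.** Patient numbers: 587 with severe disease at 50% adoption (section 8.5: "n=587 for patients with severe disease and n=176 for patients with inhibitor at the end of this 6-year study"); 216 in the last interim report (8.5); 34 and 11 with moderate disease at 15% and 5% adoption (Table 1). The person-year formula is that of 8.7.1.

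**Assumptions.** Event counts, mean exposure, and the groups of 5 patients are not in the protocol.

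**Formulas**, with N patients, x patients with the event and mean exposure T years:
- PY = N·T − x·T/2.
- (a) Binomial, n = patients, unscaled: upper limit = 0.975 quantile of Beta(x+1, N−x). For x = 0 this is 1 − 0.025^(1/N).
- (b) Limit (a) multiplied by N/PY.
- (c) Binomial, n = person-years: 0.975 quantile of Beta(x+1, PY−x), which exists only if PY > x.
- Exact Poisson (Garwood): χ²(0.975; 2x+2)/(2·PY). This is 3.689/PY for x = 0, 5.572/PY for x = 1 and 8.767/PY for x = 3.

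**Upper 95% limits per person-year**

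| Assumed case | PY | Rate | (a) | (b) | (c) | Poisson |
|---|---|---|---|---|---|---|
| 587 patients, 3 years, x = 0 | 1,761 | 0 | 0.0063 | 0.0021 | 0.0021 | 0.0021 |
| 587 patients, 2 years, x = 3 | 1,171 | 0.0026 | 0.0149 | 0.00745 | 0.00747 | 0.00749 |
| 216 patients, 540 days, x = 1 | 318.6 | 0.0031 | 0.0255 | 0.0173 | 0.0174 | 0.0175 |
| 34 patients, 1 year, x = 3 | 32.5 | 0.092 | 0.237 | 0.248 | 0.247 | 0.270 |
| 11 patients, 1 year, x = 1 | 10.5 | 0.095 | 0.413 | 0.432 | 0.428 | 0.531 |
| 5 patients, 2 years, x = 0 | 10 | 0 | 0.522 | 0.261 | 0.308 | 0.369 |
| 5 newborns, 28 days, x = 1 | 0.345 | 2.90 | 0.716 | 10.4 | none | 16.2 |

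In the last row PY = (5×28 − 14)/365.25 = 126/365.25 = 0.345, and the rate is 1/0.345 = 2.90.

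**Reading the table**
- Reading (a) is off by about the mean exposure in years in the large cohorts: 0.0063/0.0021 = 3.0 at 3 years, 0.0149/0.00749 = 2.0 at 2 years and 0.0255/0.0175 = 1.46 at 540 days (1.48 years). With exposure well under a year the error reverses. In the newborn case (a) runs from 0.005 to 0.716 and excludes its own point estimate of 2.90.
- Readings (b) and (c) agree with Poisson within about 1% for 587 or 216 patients.
- In small groups (b) and (c) are too low: by 8 to 9% for 34 patients, about 19% for 11 patients (0.43 against 0.53), and 16 to 29% for 5 patients over 2 years (0.31 and 0.26 against 0.37).
- Reading (c) has no upper limit when events exceed person-years.

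**The case against.** The strongest reply is that the numerator counts patients with a first event, censored afterwards, so it cannot exceed N. A binomial model for that count is natural and can be converted to a rate. Poisson limits are not strictly exact here either, because the person-years are imputed and depend on the event count. Both points are fair. The conversion, however, is not multiplication by N/PY. With equal exposure T and a constant rate, a proportion p corresponds to a rate of −ln(1−p)/T. For 5 patients, 2 years and no events this gives −ln(1−0.5218)/2 = 0.369, the Poisson value. For 11 patients, 1 year and 1 event it gives −ln(1−0.4128) = 0.532, against 0.531. So the binomial model, properly converted, supports the Poisson limit, and 8.7.1 specifies no conversion.

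A second reply is that little depends on the choice. The study is descriptive, point estimates do not change, and the proportion is reported as well. This stands and limits the consequence to how precision is reported.

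Two stronger readings are tempting. A reader might infer that the primary intervals are wrong throughout, with whole-cohort upper limits two to three times too high. That follows only if patients are n and nothing is rescaled, which 8.7.1 permits but does not state. A reader might also infer gross errors for newborns as a matter of course. That requires capping each newborn's exposure at 28 days. Section 8.3.2 lists age as a baseline variable, with baseline at the start of emicizumab. This suggests grouping by age at start, so that later exposure would count too. Section 8.7 does not settle the point. More events than person-years is also unlikely for rare events.

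**Conclusion.** Wrong as written: the interval prescribed for the primary rate belongs to a different measure, and its n is undefined. The size depends on how an analyst fills the gap. Used unscaled with patients as n, the limits are off by roughly the mean exposure in years, two- to threefold at 2 to 3 years. Used with person-years as n, or rescaled by N/PY, the whole-cohort limits are practically right. The upper limits are then about 8 to 29% too low in the small groups examined (5 to 34 patients, 1 to 2 years each), which is the falsely reassuring direction. An interval without an upper limit is possible but needs very short total exposure. All these sizes rest on assumed exposure and event counts. The mismatch itself rests only on the text of 8.7.1.

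**What to change.** In 8.7.1, replace the closing sentence on intervals with: *For each incidence rate, an exact Poisson (Garwood, chi-square based) 95% confidence interval will be computed from the number of patients with the event and the person-years of exposure.* In 8.7.2, state that exact binomial (Clopper-Pearson) intervals apply to the incidence proportions only.

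The cost is one replaced sentence and one clarification. Both inputs, the count and the person-years, already come from the aggregate registry reports, so no new data are needed. Point estimates and study size do not change.

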### **8.7.2            Secondary analyses:**

- Annual incidence proportion of AE of interest (TMA, TE, and anaphylaxis) among patients exposed to emicizumab will be estimated as the number of patients who were treated with emicizumab and developed the AE, divided by the number of patients who are exposed to emicizumab. The incidence proportion will be calculated overall and by age and status of inhibitor as well as by severity for patients without inhibitors.
- For each AE of interest (TMA, TE, and anaphylaxis), the following proportions will be calculated, together with the corresponding 95% confidence intervals:
  - Annual incidence proportions of the AE among patients treated with emicizumab and concurrently with each of the following drugs: aPCC, rFVIIa, and FVIII product.
- Annual number and percentage of each of the other adverse events reported to PedNet will be presented. Currently, in addition to TE, TMA, and anaphylaxis, these events may include: new inhibitors, allergic reactions, local subcutaneous reaction, other AEs including unexpected poor efficacy.
- ABRs: Estimates for the ABR are based on a negative-binomial model adjusted for age group and inhibitor status. The negative-binomial models each use the “total number of bleeds” (for each specified type of bleed) as the outcome and the model is offset by the “total duration of follow-up” since first exposure to emicizumab.

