#### RATIONALE AND BACKGROUND

Hemophilia A is an X-linked recessive bleeding disorder characterized by deficiency or absence of blood coagulation factor VIII (FVIII), which leads to a lifelong bleeding tendency.

Primary prophylaxis has proven to minimize bleeding events and complications and has become standard-of-care among pediatric patients.

Although effective when optimally administered, prophylaxis with intravenous (IV) FVIII infusion can be accompanied by significant burden of treatment with impact on the quality of life of both patients and their caregivers. Furthermore, the development of neutralizing antibodies (inhibitors) against FVIII occurs in up to 30% of patients after exposure to therapeutic FVIII concentrates.

Emicizumab (also known as Hemlibra®) is a humanized monoclonal modified immunoglobulin G4 antibody that bridges activated factor IX (FIX) and factor X to restore the function of missing activated FVIII needed for effective hemostasis. Given that emicizumab has no structural relationship to FVIII, its efficacy is not affected by the presence of FVIII inhibitors and is not expected to induce or enhance the development of inhibitors to FVIII or to other coagulation factors. Emicizumab has been evaluated in many clinical trials and approved by multiple countries.

Two important risks have been identified with the use of activated prothrombin complex

concentrate (aPCC) in patients treated with emicizumab prophylaxis: TEs and TMA. Thromboembolic events not associated with concomitant use of aPCC has been identified as an important potential risk. In addition, anaphylaxis, anaphylactoid, or systemic hypersensitivity reactions were considered as potential safety risks based on the class of biological drugs.

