## **8. RESEARCH METHODS**

### **8.1 STUDY DESIGN**

This is a non-interventional (NI) secondary data use Post-Authorization Safety Study (PASS) relying on data collected as part of the PedNet Registry. PedNet Registry will extract data (e.g., all variables) indicated in this protocol, perform the statistical analysis and provide results to the Marketing Authorization Holder (MAH) as an aggregated report. Based on this, the MAH will generate an annual PASS report and submit it to the Pharmacovigilance Risk Assessment Committee (PRAC) and/or include the annual report in the periodical benefit risk evaluation report (PBRER) depending on the time of availability of the reports.

PedNet is a multicenter, observational research database that includes patients with FVIII/IX levels < 25 IU/dL born after 1 January 2000 and treated in one of the participating Hemophilia Treatment Centers (HTCs). At the time of protocol amendment, 32 centers from 19 countries are participating in the Registry. The goal of the Registry is to include full cohorts of all consecutive patients diagnosed and treated in each center of which information on treatment and outcomes (e.g., inhibitor development, bleeds) is collected from the time of hemophilia diagnosis or time of first treatment. To prevent selection bias, patients referred to a center after development of inhibitors are not included in the database.

Data included in the Registry is collected using electronic case report forms (eCRFs). Baseline data that pertains to mode of delivery, neonatal events, diagnostic symptoms, FVIII/IX gene mutation, and family history of hemophilia and inhibitors is collected. All centers collect detailed data on treatment and outcomes (including inhibitor development and bleeds) of patients with hemophilia during the first 50 days of exposure to coagulation factor concentrate products. Following this, the centers continue to collect information at least annually until the patient reaches the age of 18. Additional information are collected regarding surgeries, hospitalizations, and AEs.

A similar level of detail is collected for patients treated with emicizumab prophylaxis. When patients treated with emicizumab receive coagulation factor concentrate products, the type of the products is recorded. It is therefore possible to evaluate the relationship between the use of FVIII/BPAs and development of TE/TMA events for patients treated with emicizumab prophylaxis.

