PedNet emicizumab specific report includes patients who are treated with emicizumab. The following data includes in the reports: number of patients treated with emicizumab, duration of emicizumab exposure, number of TE, TMA, anaphylaxis, and any other AEs,

ABR for treated bleeds, percentage of zero bleeds, ABR for joint bleeds, ABR for soft tissue bleeds, ABR for major or minor bleeds, number of patients which have used bypassing aPCC agents when treated with emicizumab, number of patients which have used FVIII products when treated with emicizumab, the number of patients used rFVII when treated with emicizumab and detailed data for patients who have developed TE, TMA or and anaphylaxis. Based on the PedNet annual report, the MAH produces the PASS report annually with the following information grouped by age and status of inhibitor as well as by severity for patients without inhibitors and/or include the results in the annual PBRRER depending on the time of availability of PedNet reports:

- Number of patients exposed to emicizumab (directly from PedNet report)
- Number of patients exposed to emicizumab who experienced TE, TMA, and anaphylaxis (calculated from PedNet report)
- Proportion and incidence of each AE of TE, TMA, and anaphylaxis among patients receiving emicizumab (calculated based on information from PedNet report)
- Number of patients exposed to emicizumab and each of the following drugs: aPCC, rFVIIa, FVIII (directly from PedNet report)
- Number of patients exposed to emicizumab and each of the following drugs: aPCC, rFVIIa, FVIII, who experienced TE, TMA, and anaphylaxis (calculated from PedNet report)
- Proportion of TE and of TMA among patients exposed to emicizumab and each of the following drugs: aPCC, rFVIIa, and FVIII (calculated based on information from PedNet report)
- Number of any other AE and number of patients with any other AE (including inhibitor development, unexpected poor efficacy, local subcutaneous reactions) reported to PedNet Registry (directly from PedNet report)
- ABR for treated bleeds, percentage of zero bleeds, ABR for joint bleeds and ABR for major bleeds (directly from PedNet report)
- Bleeds count for soft tissue bleeds and minor bleeds

PedNet performs annual data extractions in January of each year. Following each data extraction, PedNet group analyzes the data according to this protocol and provide the MAH with Annual Emicizumab-Specific Reports.

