## **8.8                    DATA QUALITY ASSURANCE AND QUALITY CONTROL**

The MAH will maintain adequate and accurate records to enable the conduct of the study to be fully documented, including but not limited to the protocol and protocol amendments. The PedNet registry is responsible for data quality assurance and quality control. All procedures including data collection, storing, monitoring, and quality assurance will be done by PedNet Registry independent of the MAH following European Guidelines and the advice from the European Science Foundation. The Registry has a central coordinator and three regional coordinators with the task of data monitoring.

Every center will be visited before start of inclusion and at the closing of the Registry. Centers will be visited regularly according to their size.

No individual patient data will be transferred to the MAH.

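### The aPCC, rFVIIa and FVIII proportions are any-use figures that overlap, and the counts requested from the registry cannot give the rFVIIa-without-aPCC or FVIII-without-bypassing-agent denominators

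*Protocol*

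**What the plan says.** Section 8.7.2 of the protocol asks, for each of TE, TMA and anaphylaxis, for "Annual incidence proportions of the AE among patients treated with emicizumab and concurrently with each of the following drugs: aPCC, rFVIIa, and FVIII product", with 95% confidence intervals. Section 8.1 lists the matching content of the annual report: the numerator is "Number of patients exposed to emicizumab and each of the following drugs: aPCC, rFVIIa, FVIII, who experienced TE, TMA, and anaphylaxis", and the reported result is "Proportion of TE and of TMA among patients exposed to emicizumab and each of the following drugs: aPCC, rFVIIa, and FVIII".

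The denominators come from the registry's report, which section 8.1 says contains the "number of patients which have used bypassing aPCC agents when treated with emicizumab" and corresponding separate counts for FVIII and rFVII users. The same report includes "detailed data for patients who have developed TE, TMA or and anaphylaxis". No count of children who used two or more products is listed, and neither section has a category for product alone, product without aPCC, or combinations.

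The purpose of the co-medication data is given in section 8.1: "It is therefore possible to evaluate the relationship between the use of FVIII/BPAs and development of TE/TMA events". The synopsis (Rationale and Background) explains why aPCC needs separate treatment: "Two important risks have been identified with the use of activated prothrombin complex" concentrate, namely TE and TMA. It then names TE without concomitant aPCC as an important potential risk of its own. Section 8.8 states "No individual patient data will be transferred to the MAH".

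**The concern.** The three product groups are not defined to exclude one another. Section 6 makes overlap plausible: it describes intensive FVIII for immune tolerance induction in children with inhibitors, and bypassing agents for bleeds in those with high titres. A child may therefore be counted under two or three products.

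The overlap is not neutral. The protocol's own risk classification turns on whether aPCC was present, yet no planned row makes that split. An event in a child who used aPCC and rFVIIa shows in the rFVIIa row as well as the aPCC row. With few events, one such child can decide whether the rFVIIa or FVIII row is zero. A reader of the annual report could then take a figure mixed with the known aPCC risk as information about the other product.

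**Working it through.** **What the protocol lets us reproduce.** It prints no product-specific figure. The nearest stated figure is the anticipated number of children with inhibitors on emicizumab in Table 1: 0.50 × 351 = 175.5, rounded to 176, which agrees. The last interim report had 80 patients with inhibitors (section 8.5). These numbers give scale only. Numbers of aPCC, rFVIIa, FVIII and dual users are not stated, so those below are assumptions.

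**Notation.** Let a = aPCC users, r = rFVIIa users, b = users of both, with one event in a child who used both.

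- As planned: aPCC row 1/a; rFVIIa row 1/r.
- Split: any aPCC 1/a (unchanged); rFVIIa without aPCC 0/(r − b); both 1/b.
- Exact 95% limits for x/n: lower = Beta⁻¹(0.025; x, n − x + 1), upper = Beta⁻¹(0.975; x + 1, n − x). For x = 0 the upper limit is 1 − 0.025^(1/n).

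**Base case, a = 10, r = 30, b = 5.**

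- aPCC 1/10 = 10.0% (0.3 to 44.5%) under both layouts.
- rFVIIa as planned: 1/30 = 3.3% (0.1 to 17.2%).
- rFVIIa without aPCC: 0/25 = 0%; upper limit 1 − 0.025^(1/25) = 13.7%.
- Both products: 1/5 = 20% (0.5 to 71.6%).
- The two planned rows together show 2 events in 10 + 30 = 40 users. In fact there is 1 event in 40 − 5 = 35 children.

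**Range of assumptions.**

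| a | r | b | rFVIIa row as planned | rFVIIa without aPCC, upper 95% limit |
|---|---|---|---|---|
| 5 | 20 | 2 | 1/20 = 5.0% | 0/18, 18.5% |
| 10 | 30 | 5 | 1/30 = 3.3% | 0/25, 13.7% |
| 20 | 40 | 10 | 1/40 = 2.5% | 0/30, 11.6% |
| 10 | 40 | 8 | 1/40 = 2.5% | 0/32, 10.9% |

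If no dual user has an event, no event appears twice.

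**Can the split be rebuilt from what the sponsor receives?**

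- Numerators: yes, provided the detailed data on event patients show the products used.
- A crude no-aPCC figure: yes. Subtract aPCC users and their events from all emicizumab patients and all events. This mixes users of rFVIIa, of FVIII and of no product.
- Denominator for rFVIIa without aPCC: no. It is r − b, and b is not supplied. With a = 10, r = 30 and one known dual user, b can be anything from 1 to 10, so r − b lies between 20 and 29. The upper limit for zero events then runs from 16.8% (1 − 0.025^(1/20)) to 11.9% (1 − 0.025^(1/29)).
- Denominator for FVIII without either bypassing agent: no. It needs the joint counts across all three products.

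**The case against.** Five points deserve weight.

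1. A reader might infer that the planned product risks are wrong, or that the rFVIIa entry for a dual user is spurious. The documents do not support this. The wording describes any use of each product, a dual user belongs in both rows, and nothing calls the figures attributable or product-alone risks. A child treated with both products was exposed to both. This stands: the fault lies only in reading a row as specific to its product. The overlap itself is inferred from plain wording, not stated.

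2. A reader might also take section 8.1 to promise a contrast of aPCC with rFVIIa. It speaks only of a relationship between FVIII or bypassing-agent use and TE/TMA, with bypassing agents pooled. This stands too, but an rFVIIa or FVIII row mixed with aPCC users still serves that aim poorly.

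3. Case detail is planned for every TE, TMA and anaphylaxis patient, and with few events the products can be read case by case. This settles the numerators, not the denominators.

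4. Replacing the rows by an ever-use hierarchy has its own bias. An event after rFVIIa alone, in a child who used aPCC at another time, would move into the aPCC row and hide the non-aPCC event that the synopsis singles out. This is a good reason to add rows beside the existing ones and to record timing, rather than to replace them.

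5. Table categories often belong in a statistical analysis plan, which is not shown. That holds for layout. But section 8.1 already fixes which counts the registry supplies, and a later table cannot be built from counts that were never requested.

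**Conclusion.** The concern holds in a limited form. The three proportions are correct as any-use figures but are not mutually exclusive, so the rFVIIa and FVIII rows cannot be read as specific to those products. The lasting defect is in the data request: with aggregate counts per product and no cross-count, the denominators for rFVIIa without aPCC and for FVIII without a bypassing agent can only be bounded.

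The size cannot be derived. Over the assumed counts, one event in a dual user puts 2.5 to 5.0% in the rFVIIa row, against 0% with upper limits of 10.9 to 18.5% once aPCC users are set aside. The intervals overlap widely, and the effect on event counts is nil if no dual user has an event. This is a secondary descriptive analysis; the primary incidence rates are untouched. The change is worth making because it is cheap and serves a distinction on which the protocol's own risk description depends.

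**What to change.** In sections 8.1 and 8.7.2:

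- Add to the registry data request the cross-count of products, that is, the number of emicizumab patients with each combination of aPCC, rFVIIa and FVIII, including none.
- Keep the three planned rows and label them *any use, not mutually exclusive*.
- Add mutually exclusive rows: any aPCC; rFVIIa without aPCC; FVIII without aPCC or rFVIIa; no concomitant product.
- For each TE, TMA or anaphylaxis case, list the products used and their timing relative to the event, so that an event after rFVIIa or FVIII alone in a child who used aPCC at another time is not hidden in the aPCC row.

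The cost is a few sentences in the protocol and one extra aggregate table from the registry each year. The exclusive cells are smaller and their intervals wider. The any-aPCC row still contains users of the other products, so the case listing is needed to read it.
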